6.2 Statistical Methods

Statistical analysis will be performed using the R statistical environment assuming 5% type I error rates. Linear mixed effects regression modeling (using the lme4 R package) will be used to assess evidence of reduced neural perseveration and reduced MADRS over time in the active neurofeedback group. Two-sample t-tests will be used to compare differences in neural perseveration and MADRS scores between the active neurofeedback and sham (yoked) neurofeedback groups after each additional session of treatment in order to establish the lowest dose of training necessary to significantly reduce neural perseveration. We will utilize multiple linear regression to assess the relationship between reduced perseveration and the reduction of MADRS scores in the active neurofeedback group while accounting for various confounds.

6.3 Control of Bias and Confounding (if applicable, typically observational study or if randomization is not taking place)

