Statistical Methodology	Linear mixed effects regression modeling will be used to assess changes in neural perseveration and MADRS over time in the active neurofeedback group. Multiple linear regression will be used to assess the relationship between reduced neural perseveration and reduced MADRS scores. Two-sample t-tests will assess group differences in task performance and symptoms after each session of treatment in order to determine the necessary dose of neurofeedback for reducing neural perseveration.

CONFIDENTIAL

Data and Safety Monitoring Plan	We have elected to utilize a Data and Safety Monitoring Board as part of our data and safety monitoring plan.
--	---

Background and Study Rationale

This study will be conducted in full accordance with all applicable University of Pennsylvania Research Policies and Procedures and all applicable Federal and state laws and regulations.

1 Introduction

Depressed individuals process negative stimuli differently from healthy participants, leading to differences in attention, memory, and cognitive control (Mogg and Bradley 2005, Mogg, Field et al. 2005, Gotlib and Joormann 2010, Sanchez, Vazquez et al. 2013, Snyder 2013, Jones and Sharpe 2017, Koster 2017). Depressed participants also tend to show larger and more prolonged neural responses to negative stimuli (Disner, Beevers et al. 2011). Relatedly, other studies have found that depressed individuals specifically have difficulty in disengaging from negative stimuli (Armstrong and Olatunji 2012, Sanchez, Vazquez et al. 2013, Mennen, Norman et al. 2019). This inability to transition out of negative states may manifest clinically as rumination--the automatic, perseverative replay of negative thoughts (Gotlib 1982, Nolen-Hoeksema, Wisco et al. 2008).

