3.4 Study Endpoints

3.4.1 Primary Study Endpoint

Our primary aim to test the efficacy of the closed loop real time fMRI neurofeedback: does this neurofeedback that specifically targets our hypothesized attentional mechanism of depression (i.e., neural perseveration of negative states) lead to reduced depression severity? The primary endpoint would then be a change in negative attention bias following training visits. Phase R61 will focus on this negative attention bias, and Phase R33 will focus on change in depressive symptom severity.

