Yes No

The following are examples of procedures involving ionizing radiation:

(Review [appendix 15.3](#) and [appendix 15.5](#))

- X-rays (examples: CT scan, chest x-ray, hand/wrist x-ray, abdomen x-ray, DEXA, pQCT, Fluoroscopy/Angiography)
- Nuclear Medicine scans (examples: FDG-PET, PET/CT, Tc-99m, SPECT, MUGA, bone scan)
- If you are unsure please contact [name] in EHRS ([contact]).

Ultrasound

Yes No

If yes, there is no protocol specific language to include but please contact [name] at: [contact]

Will your study be using CT Scans? (CACTIS is the appropriate contact for studies involving CT scans)

Yes No

Studies involving Nuclear Medicine: Will subjects be undergoing any of the following procedures specific to research:

MUGA

(See Nuclear Medicine-Muga Scan)

PET/CT Scan

(See PET/CT Scan)

Bone /DXA

(See Bone Scan)

Check off all of the following procedures that will be performed in your research- each option you select will link to the template language document:

Apheresis/plasma exchange

CONFIDENTIAL

- [Leukapheresis](#)
- [Bone Marrow Biopsy or Aspirate](#)
- [Use of AP clinical specimens](#)
- [Biopsies- check those which apply](#)
- [Blood draw](#)

5.1 *Pre-Training Visit*

The pre-training visit will include screening procedures.

Participants will be recruited, consented, and evaluated. They will also complete MRI safety screening forms and self-report medical history. This includes completing informed consent. Each patient's medical history is reviewed by [name] and, when clinically indicated, a physical examination and appropriate laboratory tests will be obtained to ensure that patients are diagnostically eligible. Consenting patients will be diagnosed with the Structured Clinical Interview for DSM-5. Participants who meet eligibility requirements will be screened using the MADRS, which will be the primary outcome measure and will have a minimum score of 16. Participants will also complete the STAI & MASQ.

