5.4.1 Data Collection and Follow-up for Withdrawn Subjects

N/A

5.5 *Early Termination Visits*

If deemed necessary to terminate a patient's participation in the study, they will be contacted by study staff to communicate this and the reason why. No other information will be collected from the terminated participant. Participant will complete end-of-study procedures as needed (receiving compensation, etc.).

5.6 *Efficacy Evaluations (only if applicable)*

Montgomery Asberg Depression Rating Scale (MADRS) will be used to examine efficacy of study intervention.

CONFIDENTIAL

5.7 ***Pharmacokinetic Evaluation (only if applicable):*** N/A

5.8 ***Genetic Testing (only if applicable):*** N/A

5.9 ***Safety Evaluation (only if applicable)***

The primary investigator will routinely monitor and evaluate study procedures for potential increased risk.

6 Statistical Plan

6.1 ***Sample Size and Power Determination***

R61 Phase: A total of 60 (n=30 active neurofeedback, n=30 sham feedback) will be enrolled. Allowing for a 10% loss of subjects, based on our preliminary data, the sample size (i.e. at least 27 patients per arm with valid post-treatment data) was chosen so that the study would have adequate power to detect between-group differences of moderate to large between group effect sizes (see power analysis below).

- For a one-sample t-test with a two-sided alternative and type I error rate of 5%, 27 participants will yield 80% power for a Cohen's $d = 0.56$. This is sufficient power to detect the effect size of $d = 0.83$ for reduction in neural perseveration found in the pilot study. For a two-sample t-test with two-sided alternative and type I error rate of 5%, 27 participants per arm will yield 80% power for a Cohen's $d = 0.86$ or larger. The statistical analysis for power determination and sample size is subject to change as data is collected over the course of the study.

R33 Phase: A total of 80 participants with MDD (n=40 real time neurofeedback, n=40 sham feedback) will be enrolled as above in a randomized controlled clinical trial. Allowing for a 10% loss of subjects, based on our preliminary data, the sample size (i.e. at least 36 patients per arm with valid post-treatment data) was chosen so that the study would have adequate power to detect between-group differences of moderate to large between group effect sizes (see power analysis below).

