- For a one-sample t-test with a two-sided alternative and type I error rate of 5%, 36 participants per arm will yield 80% power for a Cohens $d = 0.53$ or larger, which is sufficient to detect the effect size of 0.93 Visit 1 to post-treatment MADRS score decrease in the pilot data (**Hypothesis 1**). For a two-sample t-test with a two-sided alternative and type I error rate of 5%, 36 participants will yield 80% power for a Cohens $d = 0.74$ or larger. **Hypothesis 2** will utilize Pearson correlation between change in MADRS and change in negative attention scores. If nonlinearity is detected, we will employ a Spearman correlation analysis. A sample size of n=36 corresponds to 80% power to detect a significant (at 5% alpha level) correlation as low as $r=0.45$, which is sufficient to detect the effect size of $r=0.48$ found in the pilot data (**Figure 1**). **Hypothesis 3** will use a two-sample t-test comparing real vs sham NF. Pilot study data indicated a change in MADRS from baseline to 3 month follow-up corresponding to Cohen's $d=0.95$. A two-sample t-test, with 36 per group, at 5% significance level, gives 80% power to detect $d=0.74$ or larger.

CONFIDENTIAL

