6.3.2 Analysis of Primary Outcome of Interest

We will use a two-sample t-test comparison of active neurofeedback vs sham to determine the effect on MADRS scores.

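### The only named longitudinal model leaves out the sham arm, section 6.1 sets the pilot effects against one-sample tests, and no between-arm test is designated for R61 target engagement

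*Combined protocol and SAP*

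**What the plan says.** **Objectives.** The Study Summary, section 2.2 and section 3.4.2 frame R61 target engagement as a pre-post change compared between real-time and sham feedback. R33 Aim 1 is a randomised comparison with sham on depression outcome. Section 2.2 makes R33 conditional on R61 succeeding.

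**Longitudinal model.** Section 6.2 names a linear mixed model that "will be used to assess evidence of reduced neural perseveration and reduced MADRS over time in the active neurofeedback group". The Study Summary has the same restriction: it is to "assess changes in neural perseveration and MADRS over time in the active neurofeedback group".

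**Between-arm tests.** Section 6.2 also specifies two-sample t-tests of active against sham, on neural perseveration and MADRS, "after each additional session of treatment in order to establish the lowest dose of training necessary to significantly reduce neural perseveration". Section 6.3.2 states: "We will use a two-sample t-test comparison of active neurofeedback vs sham to determine the effect on MADRS scores". Section 3.4.1 adds that "Phase R33 will focus on change in depressive symptom severity", and section 5.1 describes MADRS as the scale "which will be the primary outcome measure and will have a minimum score of 16".

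**Power, section 6.1.** For R61, a one-sample test with 27 participants is said to be sufficient for d = 0.83 "for reduction in neural perseveration found in the pilot study"; a two-sample figure of 0.86 for 27 per arm follows. For R33, a one-sample test with 36 participants has a detectable effect of 0.53, "which is sufficient to detect the effect size of 0.93 Visit 1 to post-treatment MADRS score decrease in the pilot data", and this is labelled Hypothesis 1. A two-sample figure of 0.74 comes next, without a label of its own, before Hypothesis 2.

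**The concern.** A change over time in the active arm mixes any effect of neurofeedback with whatever would have happened under sham. The sham arm is randomised in order to remove that component, and the mixed model does not use it.

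The power section has a related gap. A large pre-post effect in a pilot shows that a one-sample test would be significant. It does not show that the between-arm test has enough power, because the between-arm effect is the pre-post effect minus the sham change, and the documents give no sham change.

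For R61 the consequence is the decision to go on to R33. Section 2.2 makes R33 depend on success, target engagement is the first R61 aim, and section 6 does not say which test settles it. For R33 the consequence is narrower: section 6.3.2 has an appropriate between-arm test, but the effect cited under Hypothesis 1 answers a different question.

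**Working it through.** **Step 1. Match each aim with the analysis assigned to it.**

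| Aim | Comparison stated | Analysis assigned in section 6 |
|---|---|---|
| R61 Aim 1, target engagement | active vs sham, pre-post | none designated |
| R61 Aim 2, lowest dose | effect by number of sessions | two-sample t-tests after each session (6.2) |
| R33 Aim 1, depression outcome | active vs sham | two-sample t-test on MADRS (6.3.2, phase not named) |
| Change over time in perseveration and MADRS | – | mixed model, active arm only (6.2, Study Summary) |

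Hypothesis 1 is not defined outside 6.1. Its link to R33 Aim 1 is inferred from its order and endpoint.

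**Step 2. Reproduce the printed detectable effects.** Inputs from 6.1: two-sided 5%, 80% power, 27 or 36 completers per arm. The noncentral t distribution is used, with noncentrality d√n and n − 1 degrees of freedom for one sample, and d√(n/2) and 2n − 2 degrees of freedom for two samples with n per arm.

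| Test | Printed d | Computed d |
|---|---|---|
| R61 one-sample, n = 27 | 0.56 | 0.560 |
| R61 two-sample, 27 per arm | 0.86 | 0.777 |
| R33 one-sample, n = 36 | 0.53 | 0.480 |
| R33 two-sample, 36 per arm | 0.74 | 0.670 |

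The first reproduces. The other three are printed too large, which is conservative and a separate matter. The computed values are used below.

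**Step 3. Between-arm power if sham does not change.** The active-minus-sham effect then equals the pilot effect.

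- R61: 0.83 × √(27/2) = 3.05, 52 df, power 84.9%.
- R33: 0.93 × √(36/2) = 3.95, 70 df, power 97.3%.

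**Step 4. Room for a sham response before power drops below 80%.**

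- R61: 0.83 − 0.777 = 0.05 SD of change.
- R33: 0.93 − 0.670 = 0.26 SD of change.

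**Step 5. Power if sham improves.** The documents give no sham change, so 0.3 to 0.5 SD is an assumed range. Between-arm d = pilot d − sham change, with the pilot d taken to be in SD-of-change units and that SD equal in the two arms.

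| Sham change | R61 d | R61 power | R33 d | R33 power |
|---|---|---|---|---|
| 0 | 0.83 | 84.9% | 0.93 | 97.3% |
| 0.3 | 0.53 | 48.1% | 0.63 | 75.1% |
| 0.5 | 0.33 | 22.2% | 0.43 | 43.6% |

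**Step 6. Are the pre and post scans defined for R61?** Section 3.3 lists the go/no-go task at the post-training session. The section 4.1 schedule, the section 5 table and section 5.2.3 do not. Section 3 lists four R61 training sessions; sections 3.3, 3.4.2, 4.1 and 5 have three. Section 5.2.1 mentions baseline scans for the active group only. The pre-post contrast that Aim 1 needs therefore has no settled endpoints.

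**The case against.** The plan does not ignore the sham arm. Its aims are comparative, 6.1 says the sample size was chosen for between-group differences and gives two-sample figures for both phases, 6.2 has between-arm tests of perseveration after each session, and 6.3.2 compares the arms on MADRS. The test after the last session could serve R61 Aim 1. The two-sample 0.74 stands directly after the Hypothesis 1 label and may be meant to belong to it. An active-arm trajectory model beside these tests is a legitimate secondary description. All of this stands, and it limits the point to a missing designation and a power argument tied to the wrong contrast.

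A reader might go further in three ways that the documents do not support.

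- *That no between-arm test exists.* Sections 6.2 and 6.3.2 contain such tests.
- *That a fall in the active arm alone would count as success.* No section makes the active-only model decisive, and that reading would contradict the comparative wording of Aim 1. The gap is that nothing in section 6 rules it out.
- *That R61 is below 80% power even with no sham change, because the pilot 0.83 is smaller than the printed 0.86.* The printed value is wrong for 27 per arm. The correct threshold is 0.777, and power at 0.83 is 85%.

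**Conclusion.** The concern holds in this limited form and should be fixed. The active-only restriction, the one-sample setting of both pilot effects, and the absence of a designated target-engagement test are plain in the text. That 6.3.2 is the R33 primary analysis is a reasonable inference, since it names neither phase nor time point; as a test it is sound.

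On size, the between-arm design is adequate if sham does nothing, and R33 keeps a moderate margin of 0.26 SD. The R61 margin of 0.05 SD is small, so even a slight sham response takes power below 80%. The power figures under a sham response rest on the assumed range and on equal SDs of change. They illustrate how sensitive the design is and do not predict the sham response.

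**What to change.** 1. **Mixed model (6.2 and Study Summary).** Fit it to both randomised arms with categorical visit, arm and visit-by-arm, as a supportive analysis. Use a covariance structure that the chosen software can fit, or robust standard errors. Label any active-arm-only change as descriptive.
2. **R33 (6.3.2 and 6.1).** State that the two-sample test decides Hypothesis 1, on change in MADRS from one named baseline visit to the post-training visit. The baseline must be named because 6.1 refers to Visit 1, while section 4.1 schedules MADRS both before training and at the first training visit. Define Hypothesis 1, tie it to the two-sample calculation, and note that 0.93 is a pre-post effect.
3. **R61 (6.2 and 6.1).** State that the two-sample active versus sham comparison of pre-post change in neural perseveration decides target engagement. Note that 0.83 is a pilot effect set against a one-sample test. Before naming the pre and post scans, the sponsor must reconcile the sections listed in Step 6 on the post-training task, the number of training sessions and baseline scans by arm.

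**Cost.** R33 needs wording only: MADRS is already scheduled and the test does not change. R61 needs wording once the schedule is reconciled. For the mixed model, check that lme4, named in 6.2, can fit the chosen covariance, or name another package. The downside is that the one-sample power would no longer support Hypothesis 1 or target engagement, and the small R61 margin for sham response becomes visible.

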3.4.2 Secondary Study Endpoints

Phase R61:

- Aim 1: Target Engagement. Response to real-time vs sham neurofeedback will be determined by pre-post change in selective attention to negative stimuli. Following behavioral and symptom assessment participants will receive 3 training sessions conducted in the fMRI scanner, during which participants will view overlaid neutral scenes and negative faces while attending to the scenes. Multivariate pattern analysis will quantify attention to the scenes vs. faces in real-time using a cloud-based framework that adjusts each subsequent image to reward or punish based on attention to the current image. Feedback will be delivered by changing the opacity of the images of the scene target vs face distractor. We have identified a potential neural locus of the negative attentional bias — the inability of MDD to escape from a brain state in which they are attending to negative face distractors even though task irrelevant, what we refer to as “neural perseveration” (higher conditional probability of staying in the same negative state vs. healthy individuals).
- Exploratory aim: Behavioral perseveration on negative stimuli. In addition to a neural target we will also explore a behavioral perseveration target using a gaze task (R61 Exploratory Aim). In that task, patients view a screen with positive, neutral and negative images. Using an eye-tracker, the amount of time that participants spend looking at negative stimuli after first fixating on those stimuli will be recorded and compared. To further support the hypothesis that understanding negative perseveration is relevant to brain mechanisms in depression, we will measure the same probability at the end of each day of neurofeedback treatment. The progressive change over time will provide further comparisons in the active vs sham groups.
- Aim 2: Determine the lowest “dose” of training necessary to reduce selective attention to negative stimuli. Neural and behavioral markers obtained after each session will be used to determine the lowest number of sessions that produce a significant effect, which will be chosen for the R33 phase.

R33 Phase:

- Aim 1: To conduct a randomized controlled trial (RCT) to compare the effect of real-time neurofeedback vs. sham on depression outcome in patients with MDD.
- Aim 2: To determine the relationship between the markers of neural perseveration established in the R61 phase and the reduction in depressive symptoms. Neural

CONFIDENTIAL

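### R61 Aim 2 calls the first significant session count the necessary dose, although no analysis tied to that choice compares the active-sham effect between session counts

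*Combined protocol and SAP*

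**What the plan says.** Three places describe the rule.

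- **Section 3.4.2, R61 Aim 2:** neural and behavioural markers "will be used to determine the lowest number of sessions that produce a significant effect, which will be chosen for the R33 phase".
- **Section 6.2** supplies the test: "Two-sample t-tests will be used to compare differences in neural perseveration and MADRS scores between the active neurofeedback and sham (yoked) neurofeedback groups", repeated as each session is completed, "in order to establish the lowest dose of training necessary to significantly reduce neural perseveration".
- **Study Summary, Statistical Methodology row:** the same t-tests are run "in order to determine the necessary dose of neurofeedback for reducing neural perseveration". Neither this row nor the R61 Aim 2 line in section 2.2 ties the dose to statistical significance.

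The error rate is set once: "Statistical analysis will be performed using the R statistical environment assuming 5% type I error rates". Section 6.1 gives the R61 sample as 27 per arm with valid post-treatment data.

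Section 6.2 also has a mixed model over time, but only for the active arm, and it is not linked to the dose decision. The plan gives no margin, no confidence-interval criterion and no contrast of one session count with another for choosing the dose.

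**The concern.** Written as a rule, the plan takes the smallest session count k whose active-versus-sham t-test has p < 0.05. To call k *necessary*, one must also conclude that k-1 sessions are not enough. The only evidence for that is p > 0.05 at k-1.

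Each t-test asks whether the effect after that many sessions is zero. None asks whether the effect after k-1 sessions is smaller than after k. A significant result at one visit and a non-significant one at the visit before can arise with no growth at all between them.

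The protocol presents R61 as the first dose-finding test of this method, and the chosen count goes into R33, planned for 80 participants. Section 5 puts each training visit at about 4-5 hours. A shorter course that already has the full effect could be passed over, and a *necessary* number of sessions reported with no evidence that the extra sessions added anything. Picking a count too early by chance, which multiplicity control addresses, is the opposite error.

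**Working it through.** **Inputs.** From section 6.1: 27 analysable per arm (30 enrolled, 10% loss) and a two-sided 5% test ("For a two-sample t-test with two-sided alternative and type I error rate of 5"%). From section 3.4.2: three training sessions. Assumed, because the documents give no value: the true effect by session, the between-session correlation (0.3 to 0.7, equal for all pairs), unit variance and a single outcome.

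**1. The plan's own figure.** Power = 1 - F(t*; df = 2n-2, noncentrality d√(n/2)), where F is the noncentral t distribution function. With n = 27, df = 52, √(27/2) = 3.674 and d = 0.86, the noncentrality is 3.16 and power is 87.3%, not 80%. At 5%, 80% power is reached at d = 0.777. The stated 0.86 reproduces at two-sided 2.5% (d = 0.860). That is a separate point and does not weaken this one: at 2.5%, misses are more frequent.

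**2. Chance that one given session is non-significant although the effect is there (5%).**

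| True d | Power | Miss |
|---|---|---|
| 0.50 | 43.8% | 56.2% |
| 0.78 | 80.3% | 19.7% |
| 0.83 | 84.9% | 15.1% |
| 0.86 | 87.3% | 12.7% |

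The 95% CI half-width for a difference at one session is t* × √(2/27) = 0.55 SD, so a non-significant session can be compatible with a moderate effect.

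**3. The rule itself.** Simulated: first session with p < 0.05 in the direction of benefit, three sessions, the same true effect at all three. Session 1 is then the right answer. Ranges run over correlation 0.3 to 0.7.

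| Constant true d | Session 1 named | Later session named (wrong) | None significant |
|---|---|---|---|
| 0.50 | about 44% | 19-31% | 25-37% |
| 0.78 | about 80% | 12-17% | 3-8% |
| 0.86 | about 87% | 9-12% | 1-4% |

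At d = 0.86 and correlation 0.3, for example, sessions 2 and 3 are named in 9.8% + 2.0% = 11.8%.

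**4. What a direct comparison would show.** The session 3 versus session 1 change in the active-sham difference uses within-person changes, with SD √(2(1-ρ)).

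- In the constant 0.5 SD trials that wrongly name a later session, this contrast is significant in only 7-9%. No growth exists there, so these are false positives. In over 90% of the wrong picks the contrast would not have supported the label.
- If the effect truly grows as 0.2, 0.5, 0.8 SD (assumed), the change is 0.6 SD. For ρ = 0.3, 0.5 and 0.7 the SD of change is 1.18, 1.00 and 0.77. The standardised change is then 0.51, 0.60 and 0.77, and power is about 45%, 58% and 80%.

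**The case against.** **The rule is only operational.** Sections 3.4.2 and 6.2 can be read as a working rule for carrying a number into R33. A reader might infer that the plan sets out to declare the passed-over counts ineffective or inferior. No section says so, and section 6.2 qualifies the dose as the one needed for a significant reduction. This stands in part. But the Study Summary and section 2.2 use the language of necessity without that qualifier, and that conclusion needs a comparison the plan does not make.

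**The 56% figure.** A reader might take 56% as the rate of wrong dose conclusions. It is the chance that one given session is missed at d = 0.5. Much of it is trials in which no session is significant, so no count is named, and section 2.2 makes R33 conditional on R61 success. The rate of wrongly naming a later count is 19-31%.

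**The effect size is assumed.** Section 6.1 claims adequate power for moderate to large between-group effects but gives no value for moderate; 0.5 SD is a conventional reading. At the protocol's 0.86 the error is 9-12%. The pilot value of 0.83 supports a one-sample test and does not establish an active-sham difference. The flat profile is also assumed. This limits the size, not the logic.

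**Other between-session information exists.** The active-arm mixed model (6.2) and the planned active-versus-sham look at progressive change in gaze (3.4.2, 5.1) do look across sessions. Neither drives the dose choice, and the first has no sham arm.

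**The simulated rule is a simplification.** Section 3.4.2 refers to neural and behavioural markers, while section 6.2 tests perseveration and MADRS, with no rule for combining them. An either-marker rule would lower the misses and a both-marker rule would raise them.

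**R33 validity.** A reader might infer that R33's active-sham comparison is biased. It is not: the consequence is a longer course than needed, and dose is a secondary objective of R61.

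**Conclusion.** The point holds as one about inference and labelling. Followed as written, Aim 2 infers that fewer sessions are insufficient from a non-significant t-test, and no analysis tied to the choice compares the active-sham effect between counts. That does not depend on any effect size.

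The size does depend on assumptions: 27 per arm, two-sided 5%, three sessions, one outcome, a constant effect from session 1 and correlation of 0.3 to 0.7. On those terms the share of trials wrongly naming a later session falls from 19-31% at 0.5 SD to 9-12% at 0.86 SD. At 0.5 SD a further 25-37% name no session.

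Multiplicity correction alone would not repair this. At two-sided 2.5% the single-session miss at 0.5 SD rises from 56.2% to 67.3%.

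The change should be made, but it concerns what Aim 2 may conclude and does not invalidate R61 or R33.

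**What to change.** In section 6.2, with matching text in the Study Summary and section 3.4.2:

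1. Add one mixed model of neural perseveration using both arms and all measured sessions, with arm, session and arm-by-session terms.
2. Report the active-sham difference after each session with its 95% CI. Report also the change in that difference between each earlier session and the last measured session, with its 95% CI.
3. Call an earlier count less effective only if the CI for that change excludes zero in favour of the later session. Otherwise describe the chosen count as the lowest at which an effect was detected, not as the necessary dose.

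**Reconcile first.** Section 3 lists four R61 training sessions; sections 3.3, 3.4.2, 4.1 and 5 give three. Section 3.3 places the go/no-go task at the post-training session, while the tables in 4.1 and 5 and the text of 5.2.3 show no scan there. The last-session contrast depends on both.

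**Cost.** Plan wording and one extra model on measurements already planned, subject to that reconciliation; no more patients, visits or scans. Power for the contrast is limited (about 45-80% under the assumed 0.2, 0.5, 0.8 SD growth), so Aim 2 may have to report that the counts could not be told apart. The change leaves the selection rule and its error rates as they are, and no session number is proposed.
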